8.1.2 Presentation of results

The individual platelet measurements will be listed by dose arm and visit including changes from Baseline (Day 1, pre-dose). Descriptive summaries (including n, arithmetic mean, median, SD, minimum and maximum) will be presented by dose arm and scheduled visit for both absolute values and changes from Baseline based on the FAS only. Summary tabulations by dose arm will be repeated for the subgroups defined in [Section 4.8](#) (based on the FAS only too).

In addition, a separate listing and summary will be presented (by visit, where applicable) including the following:

- *Response by visit and over all visits
- Time to Response
- Duration of Response
- *Complete Response by visit and over all visits
- Time to Complete Response
- Duration of Complete Response
- *Platelet Count $\geq 50 \times 10^9/L$ by visit and over all visits
- Time to Platelet Count $\geq 50 \times 10^9/L$
- Duration of Platelet Count $\geq 50 \times 10^9/L$
- Maximum value
- Maximum Increase from Baseline
- Baseline-corrected AUEC

*All the above variables will be included in the listing. The number and percentage of responders (for variables denoted with an asterisk) will be tabulated separately as described in [Section 8.1.3.3](#).

Summary tabulations by dose arm will be repeated for the subgroups defined in [Section 4.8](#) (based on the FAS only).

Mean and mean change from Baseline platelet values will be plotted versus scheduled visit by dose arm with all dose arms overlaid on the same plot. Similar plots will be provided for response rate over time (response, complete response and platelet count $\geq 50 \times 10^9/L$). Mean median, mean change and median change from Baseline total IgG results will be plotted over time by dose arm with all dose arms overlaid on the same plot.

Individual platelet and total IgG (including IgG subclasses, measured by ACM Global Central Laboratory) concentrations will be displayed graphically over time (Day 1 to Day 85 for Dose Arm 1; Day 1 to Day 71 for Dose Arm 2; Day 1 to Day 64 for Dose Arm 3 and Day 1 to Day 57 for Dose Arms 4 and 5) for each subject (linear scale). The platelet and total IgG concentrations will be overlaid on the same plot (discrete y-axes) with separate plots for each subject (2 lines per plot). Additional plots will be presented with the platelet and IgG subclasses overlaid on the same figure (5 lines per plot). All plots will include a vertical reference line to indicate when the last dose was administered for each subject. The mean (and median in a separate plot) change from baseline in platelet and the mean (median) change from baseline in total IgG concentrations will be overlaid on the same plot (discrete y-axes) with separate plots for each dose arm (2 lines per plot).

In addition scatter plots will be presented showing the Maximum value for platelet count versus the corresponding total IgG i.e., the value of total IgG at the time of the Maximum platelet value. All subjects will be included on the same plot with distinct symbols to distinguish the dose arms. This plot will be repeated for the Maximum platelet value versus percentage change in total IgG i.e., the percentage change from Baseline in total IgG at the time of the Maximum platelet value.

8.1.3 Statistical analysis of platelets

8.1.3.1 Analysis of maximum increase from Baseline

In order to investigate if the average maximum increase from Baseline in platelet count is greater than zero, for dose arms with ≥ 10 subjects, a 1-sided one sample t-test will be performed at the 5% level. For each dose arm the following null and alternative hypotheses will be tested:

- H_0 : Average maximum increase from Baseline within dose arm is less than or equal to zero
- H_1 : Average maximum increase from Baseline within dose arm is greater than zero

An assessment of the distribution of the maximum increase from Baseline in platelet count will be performed prior to the statistical analysis in order to check the validity of the proposed parametric analysis method. This will be based on visual inspection of histograms and quantile-quantile plots for each dose arm which will be included as part of the statistical appendices. If the data show a departure from normality, a non-parametric Wilcoxon signed rank test (1-sided) will be applied in addition to the t-test.

If the data are deemed to be normally distributed a parametric analysis will be performed using a one sample t-test. The mean maximum increase from Baseline, the 90% CI and the p-value obtained from the statistical analysis will be tabulated. In order for the null hypothesis (H_0) to be rejected the p-value must be less than 5%.

Analyses will be performed for the FAS and repeated for the PPS.

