2.4 Determination of sample size

The sample size of 15 subjects in Dose Arms 1 and 2, is mainly based on the efficacy objective of the study. In addition, the inclusion of 15 subjects in Dose Arms 1 and 2 will ensure that sufficient data are available to form conclusions about the safety of administering UCB7665. Based on the safety data from Dose Arms 1 and 2, the sample size of 6 to 12 subjects in Dose Arms 3, 4 and 5 were judged to be sufficient in order to explore subjects' safety and IgG reductions under different dose regimens and is not based on a formal sample size calculation.

For Dose Arms 1 and 2 an approximate sample size calculation for the efficacy variable "maximum increase from Baseline in platelet count" shows that 15 subjects would be sufficient to show a change from Baseline with 1-sided testing at 5% and power of 80%. The anticipated change is based on an assumed Baseline average of $25 \times 10^9/L$ and a clinically meaningful maximum value of $100 \times 10^9/L$. The calculation made use of platelet count data presented in a publication by Robak (Robak et al, 2009), but it is approximate as maximum changes from Baseline for individual subjects were not available, necessitating the use of the maximum average platelet count instead. The standard deviation (SD) is taken from visual inspection.

With 15 subjects, the responder endpoints will confirm a true 50% response rate, in excess of the maximum 15% anticipated with no treatment benefit, with power in excess of 80%.

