8.1.1 Definition of variables

The main efficacy variable is defined as the following:

- **Maximum Increase from Baseline:** the Maximum Increase from Baseline (Day 1, predose) is defined as the highest positive change from Baseline during the study. In the event that the platelet count was to decrease during the study the Maximum Increase from Baseline may be negative and would correspond to the smallest decrease from the Baseline value

The following additional variables will be defined for the platelet count, the calculation rules for which are provided in the section immediately below:

- **Response:** a platelet count $\geq 30 \times 10^9/L$ and at least 2-fold increase from the Baseline value, by visit, and at any timepoint during the study
- **Time to Response:** the first time that a given response is achieved during the study. Thus, in the event that the platelet count was to increase above the threshold level, decrease below the threshold level, and subsequently increase again the time to response would be to the first time the definition of response was achieved. The time to response will be calculated in days and presented to 1 decimal place in the listings.

Time to response (days) = Date/time of first response – Date/time of first dose of UCB7665

- **‘No’ or ‘Loss of’ Response:** a platelet count $< 30 \times 10^9/L$ OR $\geq 30 \times 10^9/L$ WITHOUT at least a 2-fold increase from the Baseline value, by visit
- **Duration of Response (including Complete Response, Response and Platelet Count $\geq 50 \times 10^9/L$):** the duration of the first time the response was achieved to first loss of response. The duration of response will be calculated in days and presented to 1 decimal place in the listings.

Duration of response (days) = Date/time of loss of first response – Date/time of first response, where “loss of first response” is defined as platelet count $< 30 \times 10^9/L$ OR (platelet count $\geq 30 \times 10^9/L$ WITHOUT at least a 2-fold increase from the Baseline value)

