8.1.3.3 Analysis of responder rate

The number and percentage of subjects achieving a Response, Complete Response and Platelet Count $\geq 50 \times 10^9/L$ will be summarized by dose arm at each scheduled post-Baseline visit. The 90% CI for the percentage of responders will be included, calculated using a Wilson approximation. The tabulation will also include an overall summary (across all visits) of the number and percentage of subjects achieving a Response, Complete Response and Platelet Count $\geq 50 \times 10^9/L$ at any time during the study. For the purpose of the tabulation the lower and upper 90% CI for the percentage of subjects will be truncated at 0 and 100% respectively.

In addition the percentage of subjects achieving a Response, Complete Response and Platelet Count $\geq 50 \times 10^9/L$ will be plotted at each post-Baseline visit. Separate plots will be presented for each response type with all dose arms overlaid on the same plot.

Analyses will be performed for the FAS and repeated for the PPS. Summary tabulations by dose arm will be repeated for the subgroups defined in [Section 4.8](#) (based on the FAS only). Percentage of days without bleeding will also be described by dose arm for each type of response (response, complete response and platelet Count $\geq 50 \times 10^9/L$). Percentage of days without bleeding is calculated using the following formula:

$$\frac{((N \text{ of visits with a SMOG score} - N \text{ of these visits where bleeding occurred}) / N \text{ of visits with a SMOG score}) \times 100$$

In case rescue medications are taken, only the data up to the start date of rescue medication will be utilized for the summary tables. Listings will contain all the data but a footnote will be included indicating the patients for which some data has been excluded from the summary tables. In case of partial dates, the imputation rules for partial dates described in [Section 4.2.7](#) will be applied.

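### The main efficacy test compares each subject's best-of-many platelet increase with zero, a null that an inert drug would also violate

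*SAP*

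**What the plan says.** Section 8.1.1 names maximum increase from Baseline as the main efficacy variable; it "is defined as the highest positive change from Baseline during the study". The value may be negative, but only if every later count lies below Baseline.

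Section 8.1.3.1 states the null as "Average maximum increase from Baseline within dose arm is less than or equal to zero". For the test, "a 1-sided one sample t-test will be performed at the 5% level", and it applies "for dose arms with ≥ 10 subjects". A one-sided Wilcoxon signed rank test is added if the data look non-normal, and the mean, 90% CI and p-value are tabulated. There is no control arm and no non-zero reference value.

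Section 2.4 sizes Arms 1 and 2 on this variable: "15 subjects would be sufficient to show a change from Baseline with 1-sided testing at 5% and power of 80" per cent. The same section says of responders: "With 15 subjects, the responder endpoints will confirm a true 50% response rate, in excess of the maximum 15% anticipated with no treatment benefit". Section 8.1.3.3 contains no test against 15%; it says "The 90% CI for the percentage of responders will be included, calculated using a Wilson approximation".

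**The concern.** The maximum of several later measurements is compared with a single earlier one. With no drug effect and no trend, each later count has the same expectation as Baseline, but the largest of them has a higher one. The hypothesis of no effect therefore does not imply a mean maximum increase of zero or less, and a small p-value is the expected result whether or not the drug works.

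Section 2.4 allows for background response in the responder endpoints (up to 15% without benefit) but makes no such allowance for maximum increase. At stake is the only formal within-arm efficacy test in the plan; the log-rank test in Section 8.1.3.2 compares arms with each other. The 80% power quoted for maximum increase is likewise power against a null that is not the null of interest.

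**Working it through.** **1. The plan's own figure.** The planned change is 100 − 25 = 75 ×10⁹/L, n = 15, one-sided 5%, power 80%. No SD is given numerically, so n = 15 cannot be reproduced directly. By the noncentral t distribution, 80% power needs a standardised effect of 0.675, so the implied SD is 75 / 0.675 ≈ 111 ×10⁹/L. Power would be 98% at SD 75, 87% at SD 100 and 71% at SD 125. The sample size is thus consistent with an SD of about 111, but this is power against a mean maximum of zero.

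**2. How many counts enter the maximum.** The AUEC rules in Section 8.1.1 give 14, 12, 11 and 9 scheduled measurements for Arms 1, 2, 3 and 4/5, including Baseline. Subtracting one leaves 13, 11, 10 and 8 post-Baseline counts.

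**3. Why the null fails without an effect.** Let Y₀ be Baseline and Y₁…Yₖ the later counts, all with the same mean. Then E[max(Y₁…Yₖ)] ≥ E[Y₁] = E[Y₀], strictly so once k ≥ 2 and the counts vary. Hence E[max − Y₀] > 0 whatever the size of the variability. With normal counts in Arm 1 the mean maximum increase is 1.67 within-subject SDs if counts are independent, and 1.18 if the lag-1 correlation is 0.8.

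**4. Rejection rate for an inert drug.** Two stationary models were simulated, with max(post) − Baseline tested by the one-sided 5% t-test. Their parameters are assumptions, because the SAP gives none.

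- Model A: log-normal counts, geometric mean 20 ×10⁹/L, between-subject log-SD 0.4, within-subject log-SD 0.1 to 0.5, serial correlation 0 or 0.6.
- Model B: normal counts, lag-1 correlation 0 to 0.99.

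| Arm | n | Later counts | Model A | Model B |
|---|---|---|---|---|
| 1 | 15 | 13 | 98.9–99.9% | 99.4–99.99% |
| 2 | 15 | 11 | 98.2–99.8% | 98.9–99.99% |
| 3 | 12 | 10 | 95–99% | 96–99.7% |
| 3 | 10 | 10 | 91–97% | 91–99% |
| 4/5 | 12 | 8 | 90–97% | 92–99% |
| 4/5 | 10 | 8 | 86–94% | 86–97% |

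In Model A the spurious mean maximum increase in Arm 1 is about +3 to +27 ×10⁹/L. The Wilcoxon test rejects 99.95% of the time (n = 15, 13 independent normal counts). The lower limit of a t-based 90% CI exceeds zero exactly when the one-sided 5% t-test rejects, so the interval behaves the same way.

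**5. Locating the cause.** Testing the change at one fixed visit on the same kind of simulated data rejects about 5% of the time. The excess comes from taking the maximum.

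**6. Where the rate falls.** In Model B, Arm 1, correlation 0.5, a decline of 1, 2 or 3 within-subject SDs by study end lowers rejection to 97%, 78% and 44%. If the rescue cut-off left every subject only 2, 3 or 4 independent counts (n = 15), it would be 48%, 80% and 93%. All remain far above 5%.

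**7. Is a responder test a safe substitute?** An exact binomial rule of at least 6 of 15 has size 1.7% at a 15% rate and power 84.9% at 50%, which agrees with the power above 80% claimed in Section 2.4. It depends on which Response is meant. Any-time Response is itself a best-of-many endpoint. In Model A (Arm 1) an inert drug gives any-time Response of 2–3% at within-subject log-SD 0.2, 13–19% at 0.3, 28–37% at 0.4 and 40–51% at 0.5. At log-SD 0.5 the rule of at least 6 of 15 rejects about 60 to 86% of the time. At a single visit the inert rate is at most about 10%.

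**The case against.** The t-test is valid for the null as literally written. A reader might infer that the test has no type I error control, but the documents do not support that: the mean maximum really is above zero when the test says so. The fault is that this null is not the hypothesis of no drug effect. This objection stands as a matter of wording and does not rescue the test.

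A reader might also infer that the trial's main conclusion or its dose-arm openings rest on this p-value. They do not. The primary objective and variable are safety (Sections 2.1.1 and 2.2.1.1), new arms are opened on DMC safety review (Sections 2.3 and 4.4), and no success rule is attached to the test. By-visit changes, by-visit response rates, Kaplan-Meier curves and AUEC are also reported. This stands, and limits the severity.

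The mismatch between Sections 2.4 and 8.1.3.3 might be read as a plan to compare the Wilson limit with 15%. No section says so; the interval is descriptive.

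Finally, the rejection rates rest on assumed variability. That is true of the exact figures. The direction needs only two or more varying counts without a downward trend, and Arms 1 and 2 stay at 98% or more across both stationary models in the table.

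**Conclusion.** The concern holds. Rejecting the null in Section 8.1.3.1 is close to certain in Arms 1 and 2 for an inert drug (about 98 to 99.9%) and likely in Arms 3 to 5 if they reach 10 to 12 subjects (about 86 to 99%). These figures assume stable untreated counts, within-subject log-SD 0.1 to 0.5 and serial correlation 0 to 0.6; steep untreated decline or early rescue reduces them. The consequence is an uninformative p-value for the main efficacy variable, a secondary objective. A large true effect would still be visible in the descriptive data. This should be fixed, but it does not undermine the primary safety analysis.

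**What to change.** - **Maximum increase:** report the mean and 90% CI descriptively, with no p-value against zero and a note that an interval above zero is expected without any effect.
- **Within-arm test:** use a one-sided 5% one-sample test of change from Baseline at one prespecified visit, for example 7 days after the last dose (Day 36, 22, 15 and 8 in Arms 1, 2, 3 and 4/5). Without a control arm it still cannot separate drug effect from background drift, but it holds about 5% when counts are stable.
- **Responder test, if wanted:** define it on Response at one named visit, not at any time. Use an exact binomial test against 15% (at least 6 of 15: size 1.7%, power 84.9% at 50%), and state that the 15% and 50% rates apply to that definition.
- **Section 2.4:** keep the power statement as the record of how n was chosen, and add that 80% power for maximum increase against zero is not power to detect a drug effect.

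The cost is SAP wording and a short program, with no new data. It would be a late change to the main efficacy test in an open-label study, after the December 2018 data evaluation meeting, and must be disclosed as such. The reported p-value will probably be less favourable.

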8.1.3.2 Analysis of time to response

The time to first response will be analyzed with the log-rank test and displayed using Kaplan-Meier curves.

Kaplan-Meier curves will be presented for the variables Time to Response, Time to Complete Response, and Time to Platelet Count $\geq 50 \times 10^9/L$. Descriptive statistics will include the p-value for the log-rank test for the equality over dose arms. The point estimate for the median number of days to response with 90% CIs will be given if estimable. Further a summary including the number and percent of censored subjects, the number of responders and total subjects by dose arm and in total will be given.

For the purpose of the analysis subjects with no response will be censored at the end of the study or at the date of withdrawal.

Analyses will be performed for the FAS and repeated for the PPS.

8.1.3.3 Analysis of responder rate

The number and percentage of subjects achieving a Response, Complete Response and Platelet Count $\geq 50 \times 10^9/L$ will be summarized by dose arm at each scheduled post-Baseline visit. The 90% CI for the percentage of responders will be included, calculated using a Wilson approximation. The tabulation will also include an overall summary (across all visits) of the number and percentage of subjects achieving a Response, Complete Response and Platelet Count $\geq 50 \times 10^9/L$ at any time during the study. For the purpose of the tabulation the lower and upper 90% CI for the percentage of subjects will be truncated at 0 and 100% respectively.

In addition the percentage of subjects achieving a Response, Complete Response and Platelet Count $\geq 50 \times 10^9/L$ will be plotted at each post-Baseline visit. Separate plots will be presented for each response type with all dose arms overlaid on the same plot.

Analyses will be performed for the FAS and repeated for the PPS. Summary tabulations by dose arm will be repeated for the subgroups defined in [Section 4.8](#) (based on the FAS only). Percentage of days without bleeding will also be described by dose arm for each type of response (response, complete response and platelet Count $\geq 50 \times 10^9/L$). Percentage of days without bleeding is calculated using the following formula:

$$\frac{((N \text{ of visits with a SMOG score} - N \text{ of these visits where bleeding occurred}) / N \text{ of visits with a SMOG score}) \times 100$$

In case rescue medications are taken, only the data up to the start date of rescue medication will be utilized for the summary tables. Listings will contain all the data but a footnote will be included indicating the patients for which some data has been excluded from the summary tables. In case of partial dates, the imputation rules for partial dates described in [Section 4.2.7](#) will be applied.

8.1.4 Rescue medication definition (after medical inspection)

In the rescue medication section of the protocol, rescue medication is defined as platelet substitution or treatment with a commercially available IVIg. In addition, the prohibited medications PLEX, dexamethasone and rituximab will also be considered as a rescue medication for analysis.

8.2 Other efficacy variables

8.2.1 ITP bleeding score

The ITP bleeding score is a consensus-based ITP-specific Bleeding Assessment Tool (ITP-BAT) based on a precise definition of bleeding manifestations and on the grading of their severity (Rodeghiero et al, 2013). The ITP bleeding score will be assessed using the ITP-BAT tool version 1.0 at the visits indicated in [Section 2.2.2](#).

Bleeding manifestations will be grouped into 3 major domains, with gradation of severity (SMOG):

- Skin (S)
- Visible mucosae (M)
- Organs (O)

Each bleeding manifestation is assessed at the time of examination and each domain is subcategorized into different types of bleeding. Severity is graded from Grade 0 to 3 or 4, with Grade 5 for any fatal bleeding. Bleeding reported by the subject without medical documentation is graded as 1. The worst bleeding manifestation since the last visit (or in the 15 days preceding the first visit) is graded for each bleeding type (within each domain), and the highest grade within each domain is reported as part of the SMOG.

The overall SMOG index will be reported as S2M2O3 for example. Intracranial bleeding will always be reported, irrespective of its grade. For example, if a female subject had S2 (subcutaneous hematoma) M2 (epistaxis) O3 (menorrhagia) and an intracranial bleeding Grade 2

(post trauma, requiring hospitalization), the SMOG index is S2M2O3 (intracranial 2). If the same subject also had intracranial bleeding Grade 3, the SMOG index is S2M2O3 (intracranial 3).

Further details regarding the bleeding types and scoring algorithms are provided in [Section 13.3](#).

The individual responses for the ITP bleeding score will be listed by dose arm and visit for those items related to the SMOG score. A separate listing will be presented for the bleeding history obtained at Screening including the date and results of any platelet counts (obtained outside the clinical study) together with any medications taken which may interfere with hemostasis; this information will not form part of the SMOG score. Details of bleeding after surgery, invasive procedures and hemostatic challenges, including platelet counts associated with such procedures will also be listed. This information will not form part of the SMOG score.

A separate listing of the grades for each bleeding type will be presented for each domain, and will include the overall score (highest grade) for the specific domain which will be used in the derivation of the SMOG.

The results for the ITP bleeding score will be summarized (n, median, minimum and maximum) by dose arm and visit (absolute values only) for each domain. In addition the number and percentage of subjects with severe or clinically relevant bleeding will be summarized at each visit. Clinically relevant bleeding is defined as follows:

- Skin (S) severity of Grade 3
- Mucosal (M) severity of Grade 2 or higher and/or
- Organ (O) severity of Grade 2 or higher

The number and percentage of subjects with absence of bleeding at each visit will also be included in the summary. Absence of bleeding will correspond to a Grade 0 for each domain.

Summaries will be presented for both the FAS and the PPS.

